9.3.2. Indicators of Adherence to RMMs

The RMMs are described in the Risk Management Plan (13). Briefly, the RMMs recommend performing laboratory screening tests prior to ritlecitinib initiation, including lymphocyte count, platelet count, hepatitis B/C, and TB; performing laboratory tests of lymphocyte count and platelet count 4 weeks after initiation, avoiding live attenuated vaccines shortly before and during treatment, and avoiding use in pregnancy and during serious infections. Ritlecitinib is currently only indicated for those age 12 years or older.

- Lymphocyte count
- Platelet count
- Screening for TB
- Screening for viral hepatitis B and C
- Live attenuated vaccines
 - o Measles
 - o Mumps
 - o Rubella
 - Others as available in data sources
- Pregnancy
- Serious infections

9.3.3. Risk Factors for Thromboembolic Events

Risk factors for thromboembolic events will be identified during the 12 months prior to and including index date:

- Age >65 years
- History of VTE
- History of arterial thromboembolism (ATE)
- Major surgery within 90 days before the index date
- Combined hormonal contraceptives
- Hormone replacement therapy
- Pregnancy
- Malignancy
- CVD

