Vaccines	Vaccine type as recorded in the Danish Health Service Registry. The registry lists vaccine pathogen e.g., MMR vaccine etc. However, it is possible to identify live vaccine based on what is used according to the Danish Health Authority. This registry records vaccines that are paid by public. Travel vaccines and vaccines paid by employer will not be recorded.	Reimbursed vaccines such as MMR, chickenpox (for patients 12 months and above), BCG, Rotavirus, varicella, Dengue, and Yellow Fever not reimbursed.	Not available	

Table 1. Preliminary Definitions of the Main Study Variables

Dragnanav	ICD 10 O about an and an fair	ICD-10 codes: O80xx-	ICD-10 O	
Pregnancy	ICD-10 O chapter codes for			
	pregnancy, NOMESCO codes	O84xx (delivery),	chapter codes	
	KMCA for Caesarean and/or	Z37xx (result of	for	
	linkage to the birth registry	delivery), O01xx-	pregnancy	
	Diagnosis codes for	O07xx (abortion and	(https://icd.w	
	pregnancy ICD-10 O chapter	other abnormal	ho.int/browse	
	(https://icd.who.int/browse10/	products of	10/2019/en#/	
	2019/en#/XV)	conception)	XV)	
	(Subject to availability check:		Linkage to	
	referral codes of prenatal	CCAM codes	birth registry	
	visits at GP from the Danish	(medical acts):	may be	
	Health Services Registry)	(delivery)	considered	
	Linkage to birth registry may	JQGD010, JQGD012,		
	be considered	JQGD004, JQGD001,		
		JQGD003, JQGD008,		
		JQGD013, JQGD005,		
		JQGD002, JQGD007,		
		JQGA002, JQGA004,		
		JQGA003, JQGA005		
		(211000,0001000		
		(termination)		
		JNJD001, JNJD002,		
		JNJP001		
		(ectopic pregnancy)		
		JJFA001, JJFC00,		
		JJJA002, JJJC002,		
		JJLJ001, JJPA001,		
		JJPC001, JQGA001		
		331 0001, 3 Q 01 1001		
		Outpatient healthcare		
		code (PRS NAT):		
		(medical termination)		
		2422, 3329, 2415,		
		2416		
Serious infection	Serious infection: ICD-10 code	I.	a hospital	
	contact with a minimum of 1 overnight stay A00-B99, D73.3, E06.0,			
	E32.1, G00-G02, G04.2, G05-G07, H00.0, H44.0, H60.0-H60.3, H66-			
	H67, H70, I30.1, I40.0, J00-J22, J32, J34.0, J36, J38.3, J39.0-J39.1,			
	J44.0, J85, J86, K04.4, K04.6, K04.7, K10.2, K11.3, K12.2, K14.0,			
	K57.0, K57.2, K57.4, K57.8, K61, K63.0, K65, K65.1, K65.2, K65.9,			
	L00-L08, L30.3, M00-M01, M46.2-M46.5, M60.0, M65.0, M71.0,			
	M71.1, M72.6, M86, N10, N11, N12, N13.6, N15.1, N15.9, N30.0			
	N30.8, N34.0, N41.2, N43.1, N45.2, N45.3, N45.4, N48.2, N61, N70,			
	N73, or N75.1, U071			
	Denmark only: Z861A (the code list will be refined in the SAP to map			

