9.7. Data Analysis

This is a descriptive study and the data will be analysed and results presented separately by country. Counts and proportions for categorical variables and mean and median with ranges for continuous variables will be calculated to address the study objectives, as below. All proportions will be reported with 95% CIs.

Data sources vary in collection of laboratory test and vaccine information (data on both laboratory tests and their results are available in Denmark; data on performed laboratory tests, but not results, are available in France; laboratory data are not available in Sweden). Data on vaccines are not available in Sweden.

Counts and proportions will be calculated for:

- 1. Patients with evidence of having performed the following laboratory tests and screenings within 3 months before index date:
 - Lymphocyte count
 - Platelet count
 - Screening for TB
 - Screening for viral hepatitis B and C
- 2. Patients with evidence of having performed the following laboratory tests at week 4 (\pm 2 weeks) after index date:
 - Lymphocyte count
 - Platelet count

- 3. Patients with evidence of having received live attenuated vaccines within 4 weeks before index date
- 4. Patients with evidence of having received live attenuated vaccines during treatment with ritlecitinib
- 5. Females in whom pregnancy, as recorded in the available data sources, overlaps with ritlecitinib use
- 6. Patients aged <12 years on the index date
- 7. Patients with a serious infection before index date
- 8. Patients with evidence of having measured risk factors and the number of measured risk factors for thromboembolic events within 12 months before index date
- 9. Patients with evidence of having measured risk factors and the number of risk factors for malignancy within 12 months before index date
- 10. Patients with evidence of having measured risk factors and the number of risk factors for CVD within 6 months before index date

The windows for ascertainment of presence of specific events may be revised to reflect the local data flow.

Detailed methodology for summary and statistical analyses of data collected in this study will be documented in a SAP, which will be dated, filed, and maintained by the sponsor. The SAP may modify the plans outlined in the protocol; any major modifications of primary endpoint definitions or their analyses would be reflected in a protocol amendment.

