9.9. Limitations of the Research Methods

The limitations of the study are included below:

- While ritlecitinib is expected to be well-captured in outpatient dispensing streams, the Swedish national health registers have minimal capture of inpatient hospital administrations and dispensings, and partial capture of outpatient hospital administrations (i.e., medications administered in outpatient clinics located in hospitals) and dispensings. Similarly, in the SNDS, hospital admissions only capture administered medications that are expensive. Thus, most medications that are dispensed or administered primarily through hospital channels will be missed. As ritlecitinib is mainly expected to be dispensed in outpatient settings, this limitation is unlikely to result in a large proportion of missed exposed patients.
- Given the use of data sources from three distinct European countries, there will be variability in capture of indicators of adherence to the RMMs across the data sources. For example, data on laboratory tests and vaccinations are not available in Sweden and may be under recorded in Denmark and France. In France, only reimbursed vaccinations are recorded, meaning some vaccines (e.g., yellow fever vaccination) will be missed. All major variabilities in data elements across data sources will be described in the SAP.
- Other limitations, which are similar across many administrative data sources, include incomplete identification of ongoing pregnancies and pregnancies ending in a

termination (as they are identifiable only by pregnancy end date); underascertainment of lifestyle factors such as smoking status and smoking history; and challenges in identifying screening for TB and hepatitis B and C in all participating countries.

- While the study includes databases from multiple regions within the EU that have adequate data quality, results from the participating countries may not necessarily be generalizable to other countries in the EU.

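### Pregnancy as a thromboembolic risk factor is sought only up to the index date, but the French codes mark only the end of pregnancy, so French women pregnant at initiation are not flagged and ended pregnancies are not separated from current ones.

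*Protocol*

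**What the plan says.** - **Window.** Section 9.3.3 of the protocol: "Risk factors for thromboembolic events will be identified during the 12 months prior to and including index date". Pregnancy is on that list with no timing of its own. Surgery on the same list does have its own: "Major surgery within 90 days before the index date".
- **Analysis.** Section 9.7 item 8 will count "Patients with evidence of having measured risk factors and the number of measured risk factors for thromboembolic events within 12 months before index date". It does not look past the index date either.
- **French codes.** The French column of Table 1 (section 9.3.7) holds delivery codes up to "O84xx (delivery"), result of delivery, abortion and other abnormal products of conception, procedure codes for delivery, termination and ectopic pregnancy, and outpatient codes for "medical termination". No antenatal code is listed.
- **Danish and Swedish codes.** These countries use "ICD-10 O chapter codes for" pregnancy, with birth-registry linkage as a possibility, so hospital contacts during a pregnancy can count.
- **Limitation.** Section 9.9 names "incomplete identification of ongoing pregnancies and pregnancies ending in a" termination, "as they are identifiable only by pregnancy end date".
- **Separate indicator.** Section 9.7 item 5 counts females whose recorded pregnancy overlaps ritlecitinib use. It is not tied to a pre-index window.

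**The concern.** Pregnancy is a time-limited state. If it is found only through a record made when it ends, a search that stops at the index date finds pregnancies that are over and passes by those that are still running. In France the risk-factor table under objective 2 would then leave out women who carry the factor when they start treatment. Wherever the 12-month lookback applies, it would also mix pregnancies that ended up to a year earlier with current ones. The count of thromboembolic risk factors per patient inherits both problems. The same report could show a French woman as pregnant during use under item 5 and as having no pregnancy risk factor under item 8, although she was already pregnant at initiation.

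**Working it through.** The protocol gives no figure on this point, so there is none to reproduce. The check is a reading of the window against the code list, followed by an illustration under stated assumptions.

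**Reading the provisions together**

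| Woman | When the French code is dated | In the window of 9.3.3? | Item 5 |
|---|---|---|---|
| Pregnant at index, pregnancy ends later | After index | No | Can be counted |
| Pregnancy ends on the index date | On index | Yes under 9.3.3; unclear under item 8, which says before index | Can be counted |
| Pregnancy ended 1 to 365 days before index | Before index | Yes | Not counted |
| Conceives after index, during use | After index | No, correctly | Can be counted |

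The first row is the miss, and in this near-complete form it is specific to France. The third row applies in all three countries, because it follows from the lookback and not from the French codes.

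**Illustration (assumptions, not document figures).** Take pregnancy length L = 70, 180 or 280 days, initiation equally likely on any day of the pregnancy, and end codes spread evenly over time. The window runs from day −365 to day 0, which is 366 days.

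1. Share of pregnancies ongoing at index that are found by code date. Only an end on day 0 qualifies, so the share is 1/L:
   - L = 70: 1/70 = 1.4%
   - L = 180: 1/180 = 0.6%
   - L = 280: 1/280 = 0.4%
2. Share of in-window end codes that belong to pregnancies already over before index: 365/366 = 99.7%.
3. Share of in-window end codes dated more than 90 days before index (days −365 to −91, 275 days): 275/366 = 75%.
4. The same rule judged against the wider meaning, pregnant at any time in the window. Pregnancies touching the window end between day −365 and day L − 1, which gives 366 + L − 1 possible end days. Those ending after index, and so missed, are L − 1 of them:
   - L = 70: 69/435 = 16%
   - L = 180: 179/545 = 33%
   - L = 280: 279/645 = 43%

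Step 4 assumes that initiation is unrelated to pregnancy. Because the risk minimization measures advise against use in pregnancy, fewer initiations during pregnancy should be expected, and the real shares in step 4 should be lower. Steps 1 to 3 are shares within a group and say nothing about how many women are in it.

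**The case against.** **The definitions are preliminary.** Section 9.3.7 calls Table 1 initial and leaves refined country-specific definitions to the SAP, and section 9.7 allows windows to be revised to suit local data flow. That is fair for the code list. But the window is stated outright in 9.3.3 and item 8, and refining end-of-pregnancy codes inside a window that closes at index cannot recover a pregnancy that ends afterwards.

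**The text does not say that the code date must fall in the window.** If pregnancy episodes were dated back from later end records, as item 5 requires in France, and then fed into 9.3.3, women pregnant at index would be found. This stands as far as it goes: the miss follows from a literal, code-date application. Neither 9.3.3 nor item 8 provides for the other reading.

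**Section 9.9 discloses the problem.** It discloses incomplete capture and the end-date reason in general terms. It does not connect them to this window, nor mention that ended pregnancies are counted.

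**Three stronger readings are tempting, and the protocol does not support them.**
- A reader might infer that the French variable is close to the reverse of its label. That presumes the label means pregnant at initiation. Read as pregnancy at some time in the past 12 months, flagging a woman who delivered in that year is correct.
- A reader might infer that a comparison between countries is invalidated. Section 9.5 rules out comparative analyses, section 9.7 presents each country separately, and section 9.9 acknowledges variable capture.
- A reader might infer that any mismatch between items 5 and 8 is an error. Item 5 covers the whole treatment episode, including the 90-day grace period in section 9.3.1, so a woman who conceives after index properly appears only there.

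**Conclusion.** The point holds in a limited form. As written and applied to code dates, the rule leaves French women pregnant at initiation unflagged unless the pregnancy ends on the index date. In all three countries it puts women whose pregnancy had ended in the same category as women pregnant at initiation. On the assumed pregnancy lengths of 70 to 280 days, it finds about 1.4% down to 0.4% of French pregnancies ongoing at index. Even under the wider meaning of pregnant at any time in the window, pregnancies that run past the index date are lost.

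The consequence is modest: one descriptive risk factor and the thromboembolic risk-factor count under objective 2. The protocol does not say how many users are pregnant, and the number is probably small. The indicator of no use during pregnancy rests on item 5 and is not bound by this window. The conclusion assumes that the French code list stays an end-of-pregnancy list and that 9.3.3 is applied to the date of the code.

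**What to change.** In section 9.3.3 and section 9.7 item 8, define the factor as a pregnancy episode overlapping the index date. Use the same episodes that item 5 needs: take end-of-pregnancy records before or after index and date them back by recorded gestational length, or by a stated assumed length where none is recorded. Let this variable enter the thromboembolic risk-factor count. Report pregnancy that ended in the 12 months before index as a separate variable. Apply both definitions in all three countries.

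The cost is a change to one definition, with a matching note in Table 1. No new data source is needed, since item 5 already calls for post-index pregnancy records in France. Two weaknesses remain and should be stated in section 9.9: gestational length has to be assumed where it is missing, and pregnancies still ongoing when the French data end will still be missed.

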	ICD-10-CM codes to ICD-10 equivalents whenever feasible)			

Table 1. Preliminary Definitions of the Main Study Variables

Risk factors for thromboe	mbolic events, malignancy or C	CVD			
Age 65 years or older	per date of birth				
History of thromboembolic events including VTE or ATE	ICD-10 codes I26, I260A I269 I82.2; I82.3, I82.8, I82.9 O22.3 Denmark only: O882D, O882E	3, O87.0, O87.1	, I81, I82.0,		
Malignancy (any, primary or secondary)	ICD-10 codes chapter C	ICD-10 codes chapter C, treatment codes if relevant	ICD-10 codes chapter C		
Major surgery within 90 days of index date	NOMESCO Classification of Operations on the nervous system: KA; Operations on endocrine organs: KB; Operations on the heart and large intrathoracic vessels: KF; Operations on respiratory organs, chest, mediastinum and diaphragm: KG; Breast surgeries: KH; Operations on digestive organs and spleen: KJ; Operations on the urinary tract, male genitalia and retroperitoneal tissue: KK; Operations on female genitalia: KL; Obstetric operations: KM; Operations on the musculoskeletal system: KN	CCAM codes for major surgery	•		
Combined hormonal contraceptives	ATC codes G03A		Not available (not reimbursed)		
Hormone replacement therapy	AT	C codes G03			
Obesity	ICD-10 codes E65				
Alcohol-related conditions	ICD-10 codes K70, F10				
Tobacco-use related conditions	ICD-1	0 codes J40-J47			
Diabetes	ICD-10 codes F	E10-E14, ATC codes A10	1		

Table 1. Preliminary Definitions of the Main Study Variables

Hypertension	ICD-10 codes I10-I15, treatment proxies			
Hyperlipidaemia	ICD-10 codes E78, treatment p	proxies, laboratory data (l	Denmark only)	
Coronary artery disease	ICD-10 codes I21-I25 Nordic Medico-Statistical Committee (NOMESCO) codes for coronary artery bypass graft (CABG) or percutaneous intervention (PCI): FNF, FNG, FNA, FNB, FNC, FND, FNE	ICD-10 codes I21-I25	ICD-10 codes I21-I25 Nordic Medico- Statistical Committee (NOMESCO) codes for coronary artery bypass graft (CABG) or percutaneous intervention (PCI): FNF, FNG, FNA, FNB, FNC, FND, FNE	
Chronic kidney disease	ICD-10 codes N18, potentially dialysis procedure codes	ICD-10 codes N18	ICD-10 codes N18, potentially dialysis procedure codes	
AA diagnosis	ICD	0-10 code L63		

Source of ICD-10 codes: Denmark and Sweden, inpatient (hospital) or outpatient (specialist visits); France, inpatient hospital encounters. ICD-10 codes with trailing letters are applicable in Denmark only.

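### Table 1 codes hormone replacement therapy as ATC G03, which contains the contraceptive code G03A, so one contraceptive dispensing counts as two thromboembolic risk factors

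*Protocol*

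**What the plan says.** Three places in the protocol bear on this.

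- **Section 9.3.3** lists the thromboembolic risk factors, under the rule "Risk factors for thromboembolic events will be identified during the 12 months prior to and including index date". "Combined hormonal contraceptives" and "Hormone replacement therapy" are two of its nine items, each standing alone.
- **Section 9.3.7, Table 1** gives the codes. The contraceptive row reads "ATC codes G03A", with one country column marked as unavailable. The HRT row gives ATC G03 and carries no exclusion.
- **Section 9.7, item 8** sets out what is reported: "Patients with evidence of having measured risk factors and the number of measured risk factors for thromboembolic events within 12 months before index date". Both the presence of factors and their count are therefore results of the study.

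Section 9.3.7 calls the Table 1 definitions initial and leaves refined, country-specific definitions to the SAP.

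**The concern.** ATC is a hierarchical classification: a longer code lies inside the shorter code that begins it. The protocol uses parent codes in this way elsewhere, for example ATC A10 as a whole group for diabetes. G03 therefore takes in G03A. Two factors meant to be distinct are defined so that one is a subset of the other.

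Two reported results are affected. The HRT proportion becomes the proportion with HRT or a contraceptive. The count of factors gives a contraceptive user two points for one drug, so a woman whose only factor is a contraceptive moves from the one-factor group to the two-factor group. Objective 2 is meant to describe how much thromboembolic risk patients carry before they start ritlecitinib, and this error makes that risk look higher and of a different kind. The sensitivity analysis in Section 9.7.1, restricted to patients with an alopecia areata diagnosis, would inherit the same error.

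**Working it through.** **The plan's own figure.** Section 9.5 gives 385 patients for P = 50% and a 95% CI 10 points wide: n = P(1 − P)z²/e² = 0.25 × 1.96² / 0.05² = 0.9604 / 0.0025 = 384.16, rounded up to 385. This reproduces and is not in dispute. It serves below only as a scale; it is a precision minimum per database, not an expected cohort size.

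**Code check.** Applying the two Table 1 rows to a patient with a single dispensing:

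| Dispensing | Contraceptive row (G03A) | HRT row as written (G03) | Factors as written | Factors with G03A excluded from HRT |
|---|---|---|---|---|
| G03A | yes | yes | 2 | 1 |
| Menopausal hormone elsewhere in G03 | no | yes | 1 | 1 |

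**Size.** Let c be the share of patients with a G03A dispensing, h the share with true HRT, and b the share with both.

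- HRT proportion as written: c + h − b. True value: h. Overstatement: c − b, at most c.
- Patients with both drugs correctly score two, so the mean factor count also rises by c − b, at most c.

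The protocol gives none of c, h or b. Assuming c between 5% and 20%, and b = 0 for the upper limit:

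| c (assumed) | HRT proportion too high by up to | Mean count too high by up to | Patients wrongly flagged, per 385 |
|---|---|---|---|
| 5% | 5 points | 0.05 | 0.05 × 385 ≈ 19 |
| 10% | 10 points | 0.10 | 0.10 × 385 = 38.5 |
| 20% | 20 points | 0.20 | 0.20 × 385 = 77 |

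**Against sampling error.** Take true HRT use of 2% or 5% (also assumed) and n = 385. The 95% CI half-width is 1.96 × √(0.02 × 0.98 / 385) = 1.4 points, or 1.96 × √(0.05 × 0.95 / 385) = 2.2 points. With no overlap between users, even c = 5% shifts the HRT estimate by more than that. For example, c = 10% and h = 2% would be reported as 12%.

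**Reach.** Neither hormone item appears in the malignancy list (Section 9.3.4) or the cardiovascular list (Section 9.3.5), so items 9 and 10 of Section 9.7 are not touched. Only item 8 is.

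**The case against.** The best defence is that Table 1 is labelled preliminary and the SAP will refine it. The study is also descriptive, only two of nine factors are involved, and no adherence indicator depends on them. This limits how much the point matters. It does not remove it. The promised refinement is general and country-specific, whereas G03 is given as a common code. Other rows say that their own lists will be refined (the Danish lymphocyte codes, the serious infection list); the hormone rows do not. A stated definition that gives a wrong count is different from a detail left for later.

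Three stronger readings are tempting, and the protocol does not support them.

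- *The 12-month window is wrong for hormones.* Surgery has its own limit ("Major surgery within 90 days before the index date"), so a reader might infer that women who stopped hormones earlier in the year are misdescribed. But objective 2 concerns characteristics before initiation, and item 8 labels its result as "the number of measured risk factors for thromboembolic events within 12 months before index date". A past-year proportion reported as past-year is not an error. A current-use rule would be a preference, of the kind an SAP may settle.
- *In Sweden, contraceptive users will appear as HRT users.* If contraceptive records are unavailable there, as the row appears to say, a search on G03 cannot return them. Section 9.4.3 describes the Swedish drug register as covering all prescribed drugs dispensed at outpatient pharmacies, which sits uneasily with that cell, but the protocol does not settle which holds. The double count can be claimed only where contraceptive dispensings are captured.
- *The HRT proportion will be mostly contraceptives.* That depends on the age and sex mix of the users, which the protocol does not give.

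**Conclusion.** The point holds as a coding error in Table 1. Wherever G03A dispensings are captured, the HRT definition includes them, the HRT proportion is too high, and one contraceptive dispensing adds two to the count of thromboembolic factors. That the error exists follows from the codes alone. Its size rests on the assumed contraceptive use: at 5-20% of patients it is up to 5-20 percentage points on the HRT proportion and up to 0.05-0.20 on the mean count, less where the same patients also use HRT. The adherence indicators and the study size are unaffected.

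**What to change.** In Table 1, replace G03 in the HRT row by the menopausal oestrogen and oestrogen-progestogen subgroups of G03, and state that G03A is excluded, so that no single dispensing meets both hormone rows. Carry the same code set into the SAP for all countries.

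The cost is an edit to a code list. It needs no additional data and no change to the windows, the study size or the adherence analyses. It is best made before data extraction starts, planned for September 2027, so that all three centres program the same definition.
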